## **8.2 Pharmacokinetic and Statistical Analyses**

Primary pharmacokinetic measures include  $T_{max}$ ,  $C_{max}$ ,  $AUC_{0-t}$ , and  $AUC_{0-inf}$ . Secondary pharmacokinetic measures include the ratio of  $AUC_{0-t}$  to  $AUC_{0-inf}$ ,  $T_{1/2}$ ,  $K_{el}$ ,  $Cl/F$  and  $V_d/F$ .

All evaluable subjects completing at least one treatment period will be included in the pharmacokinetic analysis.

Descriptive statistics will be used to summarize pretomanid plasma concentrations at each sampling time point and for derived plasma PK parameters, as applicable. Statistics include sample size (n), mean, SD, percentage coefficient of variation (%CV), geometric mean, median, minimum, and maximum.

For each participant, pretomanid plasma concentration-time data will be graphically presented. Similarly, graphs of the mean plasma concentration-time profiles and overlay graphs with combined individual plasma concentration-time profiles will be produced. Additionally, pharmacokinetic parameters may be explored graphically.

The bioavailability of 4 x 50 mg dispersible tablets relative to the 200-mg reference tablet will be determined separately for each panel using a mixed model with the log transformed PK parameter ( $C_{max}$ ,  $AUC_{0-t}$ , and  $AUC_{0-inf}$ ) as response variable; sequence, period, and treatment as fixed effects; and participant as random effect.

The effect of dose on the relative bioavailability of the dispersible tablet will be determined separately for each panel using the same model as above.

The effect of food on the relative bioavailability of pretomanid will be determined comparing, across panels, each formulation and dose taken after eating breakfast versus

Protocol Pa-824-CL-011 V1.0

the same formulation and dose taken in fasted conditions using a mixed model with the log transformed PK parameter as response variable; panel, sequence, period, treatment, and panel-by-treatment interaction as fixed effects; and participant as random effect.

The  $T_{max}$  of pretomanid for each of the formulations will be descriptively compared.

Other statistical models and/or population pharmacokinetic modelling may also be used for further data interpretation.

Pharmacokinetic calculations will be performed using appropriate software.

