**Table 1: Treatment Schedule**

Sequence (n=24 subjects per panel)	Treatment Periods			
	Period 1	Period 2	Period 3	Period 4
ABCD	A	B	C	D
BDAC	B	D	A	C
CADB	C	A	D	B
DCBA	D	C	B	A

Treatment A (reference) = 200 mg given as a single 200 mg tablet (using the immediate release formulation), orally administered.

Treatment B (test) = 200 mg given as four 50-mg tablets (using the dispersible pediatric formulation), orally administered.

Treatment C (test) = single 50-mg dispersible tablet, orally administered.

Treatment D (test) = single 10-mg dispersible tablet, orally administered.

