## 6.10 Statistical Analyses of Pharmacokinetic Data

### 6.10.1 Relative Bioavailability

The bioavailability of 4 x 50 mg dispersible tablets (Treatment B) relative to the 200-mg reference tablet (Treatment A) will be determined separately for each panel using a mixed model with log transformed PK parameters ( $C_{max}$ ,  $AUC_{0-t}$ , and  $AUC_{0-inf}$ ) as response variable; sequence, period, and treatment as fixed effects; and subject as random effect. The effect of dose on the relative

QMD Ref: Worldwide-TMP-ST-006-4.0 Effective: 12Aug2019	Governing QMD: Worldwide-SOP-ST-001
Confidentiality Statement	
This document is the property of Worldwide Clinical Trials Inc. and may not be duplicated, copied, altered or removed from company without prior approval from Worldwide Quality Assurance or in compliance with Worldwide Standard Operating Procedures.	

Worldwide Clinical Trials Controlled Quality Management Document		
 WORLDWIDE CLINICAL TRIALS	Sponsor: Protocol Number:	TB Alliance Pa-824-CL-011
STATISTICAL ANALYSIS PLAN – PHASE 1		

bioavailability of the dispersible tablets (Treatments B, C, and D) will be determined separately for each panel using a power model (Smith, 2000) of the following general form,

$$\ln(\text{PK}) = \ln(\beta_0) + \beta_1 \cdot \ln(\text{Dose}) + \varepsilon,$$

Where

PK is the pharmacokinetic parameter tested (e.g.  $C_{\max}$  or AUC)

$\ln(\beta_0)$  is the y-intercept,

$\beta_1$  is the slope (a value of  $\beta_1 \approx 1$  indicates linearity), and

$\varepsilon$  is an error term

The estimate of  $\beta_1$  with the 90% CIs will be reported along with the dose range for proportionality.

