## 7 CHANGES TO PLANNED PROTOCOL ANALYSIS

No changes to the planned analyses have been identified.

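### The dose effect rests on one power-model slope over a 20-fold range, an unrecorded change from the protocol with no stated rule for proportionality

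*SAP*

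**What the plan says.** Assessing how dose affects the bioavailability of the dispersible formulation, fed and fasted, is a secondary objective in both documents. Protocol 8.2 says the effect "will be determined separately for each panel using the same model as above". That model, given there for the 4 x 50 mg versus 200 mg comparison, has sequence, period and treatment as fixed effects and participant as a random effect, on log-transformed Cmax and AUCs.

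SAP 6.10.1 keeps that model for Treatment B versus A. For the dose effect it fits, in each panel, ln(PK) = ln(beta0) + beta1 x ln(Dose) + error to Treatments B, C and D. The form as printed has no subject, period or sequence term. The reading rule is that "a value of $\beta_1 \approx 1$ indicates linearity". The slope estimate "with the 90% CIs will be reported along with the dose range for proportionality". The SAP gives no limit for closeness to 1, no interval the CI must meet, no way of deriving the dose range and no lack-of-fit check.

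Under SAP Table 1, B is "200 mg given as four 50-mg tablets (using the dispersible pediatric formulation"), C is a single 50-mg dispersible tablet, and "Treatment D (test) = single 10-mg dispersible tablet, orally administered".

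The planned dose-effect outputs are Tables 14.4.6 and 14.4.7 and Listing 16.2.6.8 (power-model output). None is described as giving a C/B, D/C or D/B comparison. SAP Section 7 states: "No changes to the planned analyses have been identified".

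**The concern.** A treatment-factor model estimates each dose level separately. A single slope reduces three levels to one number and assumes that log exposure is straight in log dose. With a 20-fold range, a slope that looks close to 1 can correspond to a large difference in dose-normalised exposure between the ends, and the middle dose has almost no influence on it.

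This matters because Protocol 1.3 describes the 10-mg and 50-mg tablets as the products for weight-adjusted dosing under 12 years, with paediatric doses chosen to match adult exposure. How the 10-mg tablet performs is something the study should report directly, with its uncertainty. The SAP leaves a slope, an undefined notion of closeness to 1, and a proportional dose range that readers cannot reproduce. Because Section 7 is silent, they would also not know that the protocol's analysis had been replaced.

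**Working it through.** The documents give no CV, power or proportionality limit, so there is no planned figure to reproduce.

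**Inputs from the documents.** Doses of 10, 50 and 200 mg (SAP Table 1) and 24 subjects per panel (SAP Section 4). **Assumptions:** complete, balanced data and residual CVs of 20%, 30% and 50%.

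**1. Scale of the slope.** The dose ratio is 200/10 = 20. Fitted dose-normalised exposure at 10 mg relative to 200 mg is 20^(1 - slope). A slope of 1.10 gives 20^(-0.10) = 0.74; a slope of 0.90 gives 20^(0.10) = 1.35.

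**2. Slope under a shortfall at one level.** The values of ln(dose), centred on their mean, are -1.535, 0.074 and 1.461, with sum of squares Sxx = 4.496. If one level has relative dose-normalised exposure R and the others are proportional, slope = 1 + (centred value x ln R)/Sxx.

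| Departure | R = 0.80 | R = 0.75 |
|---|---|---|
| 10 mg only | 1 + (-1.535 x -0.223)/4.496 = 1.076 | 1 + (-1.535 x -0.288)/4.496 = 1.098 |
| 50 mg only | 1 + (0.074 x -0.223)/4.496 = 0.996 | 1 + (0.074 x -0.288)/4.496 = 0.995 |

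**3. What the slope's 90% CI would show for a 10-mg shortfall.** Residual SD = sqrt(ln(1 + CV^2)); SE = SD/sqrt(24 x 4.496); the half-width is t x SE, with 47 degrees of freedom if subject is in the model. The chance that the CI includes 1 comes from the noncentral t distribution.

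| Residual CV | SE | CI at slope 1.076 | Includes 1 | CI at slope 1.098 | Includes 1 |
|---|---|---|---|---|---|
| 20% | 0.019 | 1.044 to 1.108 | 1% | 1.066 to 1.130 | under 0.1% |
| 30% | 0.028 | 1.029 to 1.124 | 16% | 1.051 to 1.146 | 4% |
| 50% | 0.045 | 1.000 to 1.153 | 50% | 1.022 to 1.175 | 31% |

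If the model is fitted as printed, without a subject term, between-subject variation enters the residual and the relevant CV moves towards the lower rows.

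**4. A 50-mg departure.** The slope moves by at most 0.005, a quarter of the smallest SE above (0.005/0.019). Neither the slope nor its CI can be expected to detect it.

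**5. What the direct ratio would show.** For D/C or D/B from the crossover model, SE = SD x sqrt(2/24). A true ratio of 0.80 would be reported as 0.80 with a 90% CI of about 0.73 to 0.88 at CV 20%, 0.69 to 0.92 at 30%, and 0.64 to 1.00 at 50%. The ratio does not remove imprecision at high CV, but it states the departure on the exposure scale instead of as a slope of 1.08.

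**6. The limit decides the verdict.** A dose-normalised ratio limit theta over 20-fold corresponds to slope limits 1 +/- ln(theta)/ln(20): 0.926 to 1.074 for 80-125%, 0.881 to 1.119 for 70-143%, and 0.769 to 1.231 for 50-200%. A point slope of 1.098 fails the first and passes the other two. None of these limits is in the documents.

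**The case against.** Several points on the other side are sound.

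- *The CI is reported.* At low to moderate CV it would usually exclude 1 when the 10-mg tablet is 20% to 25% low, and calling that linear would sit badly with the SAP's own output. This stands, so a reader who infers that a shortfall would be reported as linear goes too far. What remains is that the SAP gives the CI no role in the conclusion, and that at higher CVs the CI includes 1 too often to be relied on.
- *The shortfall is visible elsewhere.* CL/F is dose divided by AUC0-inf and is summarised by panel and treatment. A 20% AUC shortfall would appear as CL/F about 25% higher (1/0.80 = 1.25). This stands, but the display is descriptive, has no ratio or interval, and says nothing about Cmax.
- *The design confounds dose and strength.* A reader might infer that the power model creates this problem and that D/C would isolate tablet strength. It would not: D versus C changes dose fivefold as well as strength, and no arm gives one dose with both strengths. D/C and D/B share the confounding; only C/B is clean, for dose.
- *The cited method may supply a rule.* The SAP cites a published power-model paper, which its reference list omits. Whether that paper sets a limit cannot be checked here, so the documents do not show that a limit will be picked after the slope is seen. They show only that no rule is stated.
- *The protocol allows other models and sets no proportionality limit.* True, but it allows them for further interpretation, which does not cover an unrecorded replacement. The SAP gives only a general form, so a subject term is not excluded; it is simply not stated.

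**Conclusion.** The point holds as a weakness of a secondary analysis. SAP 6.10.1 departs from Protocol 8.2 without Section 7 saying so, gives no rule for the proportional dose range, and relies on a summary that could be read as linear despite a material departure. A 20% to 25% shortfall of the 10-mg tablet alone gives a slope of only 1.08 to 1.10, and the same shortfall at 50 mg alone leaves it at about 1.00.

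The slopes follow from the doses alone, given balanced data. The detection probabilities rest on the assumed CVs of 20% to 50%: for a 20% shortfall at 10 mg, the CI includes 1 in about 1% to 50% of trials. The documents do not support saying that a shortfall would go unseen, that the power model is the source of the dose and strength confounding, or that a particular acceptance limit is required.

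**What to change.** In SAP 6.10.1, make the protocol's mixed model (sequence, period, treatment; random subject) the main dose-effect analysis. Report dose-normalised geometric mean ratios with 90% CIs for C/B (dose at constant tablet strength), D/C and D/B, noting that the last two combine dose and strength. Each treatment has one dose, so dose-normalising only shifts the log contrasts, by ln 4, ln 5 and ln 20. The fit already made for B versus A therefore supplies them.

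Keep the power model as support, with a subject random effect, and state in advance the rule for the proportional dose range. Slope limits of 0.926 to 1.074 are one option and are not required. With 24 subjects, a truly proportional drug would meet that criterion about 97% of the time at CV 20%, 66% at 30%, and never at 50%, so the choice needs thought.

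Record the model change in SAP Section 7 and add the cited method to the reference list. The SAP supplement shows that the database has been locked. If the text can no longer change, SAP Section 6 allows additional tables with justification in the study report; any limit adopted then should be labelled as set afterwards.

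The cost is wording plus three contrasts per parameter and panel (3 x 3 x 2 = 18 ratios), with no new data. The downside is a possibly less favourable statement on dose linearity.

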### 6.10.2 Food Effect

The effect of food on the relative bioavailability of pretomanid will be determined by comparing Panel 1 (Fed) to Panel 2 (Fasted) for each treatment using an ANOVA model with panel as the fixed effect. For informational purposes, the food effect will also be evaluated using the following ANOVA models:

- 1) Using data from the 4 x 50 mg dispersible tablets (Treatment B) and the 200-mg reference tablet (Treatment A) from both panels the ANOVA model will include panel, treatment, and the panel by treatment interaction term as fixed effects to determine if the food effect differs across the two treatments. A p-value equal to or smaller than 0.05 for the panel by treatment interaction term indicates that the food effect differs between the treatments. If the p-value is greater than 0.05 an ANOVA model with panel and treatment as the fixed effects will be used to determine the common food effect for Treatments A and B (Panel 1 vs Panel 2).
- 2) Using data from the dispersible tablets (Treatments B, C, and D) from both panels the ANOVA model will include panel, treatment, and the panel by treatment interaction term as fixed effects to determine if the food effect differs across the dispersible tablets. A p-value equal to or smaller than 0.05 for the panel by treatment interaction term indicates that the food effect differs among the dispersible tablets. If the p-value is greater than 0.05 an ANOVA model with panel and treatment as the fixed effects will be used to determine the common food effect for the dispersible tablets (Panel 1 vs Panel 2).

QMD Ref: Worldwide-TMP-ST-006-4.0 Effective: 12Aug2019	Governing QMD: Worldwide-SOP-ST-001
Confidentiality Statement	
This document is the property of Worldwide Clinical Trials Inc. and may not be duplicated, copied, altered or removed from company without prior approval from Worldwide Quality Assurance or in compliance with Worldwide Standard Operating Procedures.	

Worldwide Clinical Trials Controlled Quality Management Document		
 WORLDWIDE CLINICAL TRIALS	Sponsor: Protocol Number:	TB Alliance Pa-824-CL-011
STATISTICAL ANALYSIS PLAN – PHASE 1		

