**Criteria for evaluation:**

*Pharmacokinetics:*

Full pharmacokinetic profiles of pretomanid will be determined up to 96 hours after each intake of pretomanid. Blood samples for analysis of pretomanid concentrations will be drawn just before drug intake (pre-dose), and at 0.5, 1, 2, 3, 4, 6, 8, 12, 16, 24, 36, 48, 72, and 96 hours post dose (15 samples per dose).

Primary pharmacokinetic measures include  $T_{max}$ ,  $C_{max}$ ,  $AUC_{0-t}$ , and  $AUC_{0-inf}$ . Secondary pharmacokinetic measures include the ratio of  $AUC_{0-t}$  to  $AUC_{0-inf}$ ,  $T_{1/2}$ ,  $K_{el}$ ,  $Cl/F$  and  $Vd/F$ .

Statistical summaries for a given period will include data from all subjects for whom it was a completed period, even those who do not complete all four periods. The primary mixed-model analyses for relative bioavailability, dose, and food will use all the data from all completed periods.

Descriptive statistics will be used to summarize pretomanid plasma concentrations at each sampling time point and for derived plasma PK parameters, as applicable. Statistics include sample size (n), mean, SD, percentage coefficient of variation (% CV), geometric mean, median, minimum, and maximum.

All data will be listed, even if not used for statistical summaries or model-based analyses. But data that do not come from completed periods will be characterized in the listing as to their deficiency.

For each participant, pretomanid plasma concentration-time data will be graphically presented. Similarly, graphs of the mean plasma concentration-time profiles and overlay graphs with combined

Protocol Pa-824-CL-011 V.1.0

individual plasma concentration-time profiles will be produced. Additionally, pharmacokinetic parameters may be explored graphically.

The bioavailability of 4 x 50-mg dispersible tablets relative to the 200-mg reference tablet will be determined separately for each panel using a mixed model with the log transformed PK parameter ( $C_{max}$ ,  $AUC_{0-t}$ , and  $AUC_{0-inf}$ ) as response variable; sequence, period, and treatment as fixed effects; and participant as random effect.

The effect of dose on the relative bioavailability of the dispersible tablet will be determined separately for each panel using the same model as above.

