#### **7.4 Indications for Subject Withdrawal**

Subjects will be free to withdraw at any time for any reason, or they may be withdrawn if necessary, to protect their health and safety or the integrity of the study data.

Subjects who are withdrawn from the study will not be replaced. Subjects in Panel 1 (fed) who do not complete the required FDA standard high-fat, high-calorie breakfast will be withdrawn from that study period.

The final report will include reasons for withdrawals. In the event of an early termination, subjects will undergo the procedures described in [Section 5.7](#).

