#### **6.2.8.3 Emesis**

Subjects that experience emesis within 4 hours of dosing will be excluded from the PK analysis for the period during which the emesis occurred.

QMD Ref: Worldwide-TMP-ST-006-4.0 Effective: 12Aug2019	Governing QMD: Worldwide-SOP-ST-001
Confidentiality Statement	

This document is the property of Worldwide Clinical Trials Inc. and may not be duplicated, copied, altered or removed from company without prior approval from Worldwide Quality Assurance or in compliance with Worldwide Standard Operating Procedures.

Worldwide Clinical Trials Controlled Quality Management Document		
 WORLDWIDE CLINICAL TRIALS	Sponsor: Protocol Number:	TB Alliance Pa-824-CL-011
STATISTICAL ANALYSIS PLAN – PHASE 1		

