#### **6.2.8.4 Unable to Complete FDA Standard Breakfast**

Subjects in Panel 1 that are unable to complete the high-calorie, high-fat FDA breakfast will be excluded from PK analysis during which the incomplete breakfast occurred.

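### SAP 6.10.2 replaces the protocol's food-effect mixed model with four panel-only ANOVAs without declaring it, giving up period adjustment and some protection against excluded profiles

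*SAP*

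**What the plan says.** Protocol 8.2 and the synopsis specify a single food-effect model fitted across both panels, with the log PK parameter as response and "panel, sequence, period, treatment, and panel-by-treatment interaction as fixed effects; and participant as random effect". The synopsis adds: "The primary mixed-model analyses for relative bioavailability, dose, and food will use all the data from all completed periods".

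SAP 6.10.2 compares Panel 1 with Panel 2 "for each treatment using an ANOVA model with panel as the fixed effect". That means four separate one-way analyses, one per treatment. Two pooled models follow, introduced with "For informational purposes, the food effect will also be evaluated using the following ANOVA models". They also contain no subject or period term, so no analysis in the SAP delivers the protocol's model. SAP 6.10.1 does keep sequence, period and random subject for Treatment B versus A.

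SAP Section 7 reads: "No changes to the planned analyses have been identified". The later SAP supplement also records no change to the text.

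The SAP's own rules create incomplete data. On the breakfast, SAP 6.2.8.4 says: "Subjects in Panel 1 that are unable to complete the high-calorie, high-fat FDA breakfast will be excluded from PK analysis". Protocol 7.4 shows that this works period by period, because subjects "who do not complete the required FDA standard high-fat, high-calorie breakfast will be withdrawn from that study period". On vomiting, SAP 6.2.8.3 says: "Subjects that experience emesis within 4 hours of dosing will be excluded from the PK analysis for the period during which the emesis occurred". SAP 6.2.8.2 (terminal-slope and extrapolation criteria) and 6.2.8.5 (predose concentration) can remove further results in either panel.

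**The concern.** The food effect for each formulation is the first-listed secondary objective, and its main analysis in the SAP is not the one in the protocol. A reader who relies on Section 7 would not know this.

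The substitution gives up two things. First, the Williams design spreads each treatment over all four periods. Without a period term, any difference between periods goes into the residual. Second, when one profile of a subject is excluded, the one-way ANOVA for that treatment drops the subject altogether. The mixed model still uses up to three other profiles, which show whether that subject tends to have high or low exposure. This matters most for the breakfast rule, because it can remove profiles from the fed panel only. At stake are the accuracy of four fed/fasted ratios and adherence to the prespecified analysis.

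**Working it through.** **No figure to reproduce.** The SAP states that the sample size has no statistical basis, and neither document gives a variance. The check therefore compares the two analyses on the actual design under stated assumptions.

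**Inputs from the documents.** 24 subjects per panel; sequences ABCD, BDAC, CADB and DCBA (SAP Table 1); 90% CIs (SAP 6.3.1); true fed/fasted ratio 2, since Protocol 1.2 puts fasted bioavailability at about half of fed.

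**Assumptions.** 24/4 = 6 subjects per sequence; log-scale SDs of 0.2-0.3 between subjects (sb) and 0.2 within subjects (sw), with sb up to 0.4 and sw 0.15-0.25 in the formula below; linear period drift of 0, 0.15 or 0.30 log units from Period 1 to 4; about 10-12% of the 24 x 4 = 96 fed profiles excluded.

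**Step 1: CI width with complete data.** Each panel has 6 subjects per period for each treatment. The period sum of squares entering the one-way residual is therefore 48 x Vp on 46 degrees of freedom, where Vp is the variance of the four period effects. The CI is widened by

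factor = sqrt(1 + Vp x (48/46) / (sb² + sw²)).

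- Drift 0.15 (0, 0.05, 0.10, 0.15): Vp = 0.003125. With sb 0.3 and sw 0.2, factor = sqrt(1 + 0.00326/0.13) = 1.012.
- Drift 0.30: Vp = 0.0125, factor = sqrt(1 + 0.01304/0.13) = 1.049.
- Over SD pairs from 0.2/0.15 to 0.4/0.25: 1.007-1.026 at drift 0.15 and 1.029-1.099 at drift 0.30.

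**Step 2: simulation.** 600 trials per scenario, one-way ANOVA against the protocol mixed model fitted by REML. The Monte Carlo standard error of the bias is about 0.25-0.4 percentage points. Ranges cover sb = 0.2 and 0.3.

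| Scenario | Bias, one-way | Bias, mixed model |
|---|---|---|
| Complete data | same estimate | same estimate (difference about 1e-14) |
| Random fed loss, about 10% | -0.2% to -0.3% (noise) | -0.3% (noise) |
| Intermittent, exposure-related, about 10% | -2.0% to -2.4% | -0.3% to -0.9% |
| Same, strong dependence, about 12% | -3.4% to -5.2% | -1.7% to -2.2% |
| Same subjects lost in all four periods, about 10% | -1.6% to -2.6% | -1.6% to -2.5% |
| Loss concentrated in late periods, drift 0.15-0.30, about 10% | -0.5% to -1.3% | -0.6% to +0.2% |

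Coverage of the nominal 90% CI:

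- One-way: about 92% with complete data and drift 0.30; about 90% under moderate exposure-related loss; 86-87% under strong dependence.
- Mixed model in the same scenarios: about 90%, 91% and 89-90%.

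With complete data and no drift, the CI half-widths at SDs 0.3/0.2 are 0.173 (one-way) and 0.174 (mixed) log units.

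**Step 3: does the protocol model carry its own risk?** A single within-subject variance pools 10 mg to 200 mg and two formulations. Suppose sb = 0.3 and sw is 0.30 for one treatment and 0.20 for the other three.

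- True variance for that treatment: 0.09 + 0.09 = 0.18.
- Pooled model: 0.09 + (0.09 + 3 x 0.04)/4 = 0.1425.
- SE ratio: sqrt(0.1425/0.18) = 0.89.
- Coverage: P(|Z| < 1.645 x 0.89) = about 86%.

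The one-way ANOVA for that treatment would keep about 90%. Restoring the protocol model with one pooled variance would therefore exchange one weakness for another.

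**The case against.** The strongest case against the point is that the consequences are hypothetical. Panel is a between-subject factor, so a random subject effect changes almost nothing for this contrast when data are complete. Breakfast ends before dosing (Protocol 5.4.1), so failing to finish it cannot result from that period's drug exposure. Protocol 1.2 reports no clinically significant PK difference by sex or body weight, which weakens the obvious indirect link. Inclusion criterion 7 admits only volunteers willing and able to eat the whole meal, so 10% loss may be too high. Panel 1 has this type of breakfast before every dose, so a subject who fails once may fail every time, and then the mixed model is no better. Period effects only make the one-way CIs wider. No decision threshold depends on the food effect.

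All of this stands as a limit on size. A reader might infer that fed-only exclusions do bias the ratios, or that the one-way CIs are generally wrong. The documents support neither: they show no link between exclusion and exposure and give no exclusion rate or period effect.

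The pooled-variance argument in Step 3 also stands. It bears on how the model should be restored, and the SAP does not offer it as a reason for the change.

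The objection does not reach the undeclared substitution. It also addresses mainly the breakfast rule. Emesis and the terminal-phase criteria act after dosing, in both panels, and can remove single profiles. Under the sequences in SAP Table 1, the 10-mg dose directly follows a 200-mg dose only in Periods 2 and 3. Any carryover losses under the predose rule would therefore tend to be uneven over periods. That is a mechanism only, since the documents give no half-life.

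**Conclusion.** The point holds in a limited form. It is certain that the SAP's main food-effect analysis departs from the protocol's and that Section 7 is incorrect in reporting no change.

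The numerical consequence is conditional and modest. It is nil for the ratios with complete, balanced data, and random exclusions cause no bias. Period effects make the CIs conservatively wide, by about 1-3% at drift 0.15 and 3-10% at drift 0.30. Bias of about -2% to -5% arises only if roughly 10-12% of fed profiles are lost intermittently and in relation to exposure; the mixed model reduces this to about -0.3% to -2%. Period-unbalanced loss combined with a period effect adds at most about -1.3% in the scenarios run. The negative sign reflects loss of higher-exposure subjects, and the opposite link would reverse it.

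A bias of this size would move a ratio of 2.00 to between 1.96 and 1.90, well inside a CI half-width of about 0.17 log units. A food effect near 2 would not be overturned, so the point should not be read as casting doubt on its existence. Every SD, drift and loss rate here is assumed, because the documents give none.

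**What to change.** In SAP 6.10.2 and Table 14.4.5, restore the Protocol 8.2 mixed model as the main food-effect analysis. Report the four Panel 1/Panel 2 geometric LS mean ratios with 90% CIs, and keep the one-way ANOVAs as a sensitivity analysis.

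Two additions go beyond the protocol's text and should be labelled as such:

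- a within-subject covariance that is unstructured or heterogeneous by treatment, also allowed to differ by panel if the model converges;
- Kenward-Roger or Satterthwaite degrees of freedom.

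If the sponsor prefers the one-way ANOVAs as the main analysis, Section 7 should declare and justify the change, and the mixed model should be reported as sensitivity. The SAP supplement was written after database lock. If the plan can no longer be amended, the same correction belongs in the study report, with the mixed model identified as the protocol-specified analysis.

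The cost is SAP wording and one model call per PK parameter on data already collected. The small downside is that the mixed model assumes a covariance structure, which the retained ANOVAs can check.
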